Protocol waivers or exemptions are not allowed with the exception of immediate safety concerns. Therefore, adherence to the study design requirements, including those specified in the outline of study procedures (Section 6.3), are essential and required for study conduct.

- Type of design: Prospective, epidemiological, interventional, multi-country, cohort study.
- Study population: A cohort of approximately 2400 infants will be included in the study at birth and followed-up up to 2 years of age. *A maximum of* 2400 children will be included in the extension and followed up to 6 years of age.
- Type of study: Self-contained.
- Data collection: Electronic case report form (eCRF).
- Biological samples (*Primary Study only*):
 - Cord Blood collected from all participating subjects, at birth.
 - Nasal swabs collected from subjects with potential LRTI.
 - Serum collected from a *sub-cohort of subjects*, *excluding* those born at a gestational age of less than 36 weeks. Sampling time points for this sub-cohort will be randomly allocated as specified in Table 1.
Table 1Blood sample collection

Time point	Seroprevalence sub-cohort Number of allocated subjects*
2 months	200
4 months	200
6 months	250
12 months	300
18 months	450
24 months	600
Total	2000

Note: Only one blood sample will be withdrawn from each subject in this sub-cohort.

*Number of subjects selected per time point is calculated based on the required number of subjects for adequate analysis considering an accumulating drop-out of subjects. Actual numbers might be less due to drop-outs and exclusion of subjects with gestational age <36 weeks.

- Duration of the study: Approximately 2 years for each participant enrolled in the primary study and an additional (approximately) 3 to 4 years for each participant enrolled in the extension study.
 - Epoch 1 (Primary Study): Begins at birth (Visit 1) and ends at the age of approximately 2 years (Visit or contact at 2 years).
 - Epoch 2 (Extension Study): Begins with the first contact for the extension study (at approximately age 2 years); ends with the contact at approximately the sixth birthday. Table 2 presents the study groups and epochs foreseen in the study.

Table 2Study groups and epochs foreseen in the study

Study Groups	Number of subjects	Age (Min/Max)	Epoch 1	Epoch 2
Primary	Approximately 2400	0 days - 2 years	Х	
Extension	Maximum 2400	Approximately 2 years to 6 years		х

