9.7.2. Secondary objectives

• To determine the total health burden of non-RSV-associated RTI with a suspicion of involvement of the lower respiratory tract.

Incidence rates will be calculated as the number of non-RSV-associated RTI with a suspicion of involvement of the lower respiratory tract over the number of children-years observations, overall and by subgroups.

Descriptive statistics of the different types of healthcare utilization will be provided (proportions, duration, etc.) among non-RSV-associated RTI with a suspicion of involvement of the lower respiratory tract, overall and by subgroups.

• To evaluate the association between RSV-associated LRTI, RSV-associated severe LRTI and RSV neutralizing antibodies in the baseline cord blood samples collected from subjects, at birth.

The impact of the level of RSV neutralizing antibodies in the baseline cord blood samples on the risk of having a RSV-associated LRTI and RSV-associated severe LRTI will be assessed through a statistical model.

Incidence rates will be calculated overall and by level of antibodies in the cord blood sample, as the number RSV-associated LRTI/severe LRTI as classified by the case definition and severity scale over the number of children-years observations.

• To determine the prevalence of RSV infection, at 2, 4, 6, 12, 18 and 24 months in a randomly selected sub-cohort of subjects by assessing antibodies in serum.

The primary analysis will be based on ATP sub-cohort for this objective.

Infection by RSV will be assessed (with 95% CI) by time point as the proportion of samples with a positive score of antibody titer after adjusting for baseline antibody results over the total number of samples.

Scores will be determined based on the measured antibody titer *vs*. the expected antibody level at the time of sampling based on the individual baseline (cord blood) value and the average, modelled decay rate.

• To assess the between calendar year variability in the incidence rates of RSVassociated LRTI.

Incidences rates will be calculated as the number of RSV-associated LRTI/severe LRTI as classified by the case definition and severity scale, over the number of children-years observations, in the subgroups of subjects recruited from months 1-6 and from months 13-18.

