9.11. Sequence of analyses

An interim analysis will be performed after data lock at the end of recruitment (expected after 18 months) or in June 2015 whichever occurs first, on the data collected for the subjects recruited in the first year of the study (approximately 1600). This interim analysis will be performed to obtain preliminary indications of the results in very young infants. These preliminary results will be used for potential adjustment of the LRTI Case

Definition and Severity Scale before final analysis, and to provide data for other relevant decision making, as soon as possible.* The results pertaining to this analysis will be descriptively reported in *an* interim statistical report.

*Based on the preliminary results of the interim analyses it was decided that the incidence rate would be more robust if all subjects completed the primary study until 2 years of age.

Final analysis will be performed on all the data collected and cleaned in the study, at the end of the extension period which is expected to occur 7 years after study start. An integrated study report presenting the consolidated analysis for the entire study duration (primary and extension study period [as applicable]) will be written and made available to the investigators.

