- The recruitment will be performed using a first application of SBIR where subjects will be entered on obtaining ICF and recruitment is controlled on the monthly recruitment rate. The aim is to attain a reasonably stable number of subjects per month over the full recruitment period in order to achieve an equal spread in the age of subjects at first exposure to an RSV season. Recruitment will be actively controlled through the SBIR system on country level according to agreed targets, actual recruitment rates, and further recruitment potential, so as to achieve a sufficient population on a regional level. With concurrent recruitment across the globe (with different seasonality) and an intended, steady recruitment over 18 months, the following population is to be included;
 - Subjects from NH during first 6 months
 - Subjects from SH during first 6 months
 - Subjects from NH during second 6 months
 - Subjects from SH during second 6 months
 - Subjects from NH during third 6 months; repeat of first 6 months NH
 - Subjects from SH during third 6 months; repeat of first 6 months SH

 In case recruitment is extended beyond 18 months, subjects recruited in the fourth 6 month period are a repeat to those recruited during the second 6 month period

Figure 3 RSV seasons in Northern and Southern Hemispheres

NH=Northern hemisphere, SH=Southern Hemisphere. Figure assumes equal recruitment targets on both hemispheres (which is not a requirement for the study).

Figure A represents recruitment in the NH and assumes RSV seasons running from November to April relative to a currently estimated time point 0 in Nov 2013.

Figure B represents recruitment in the SH and assumed RSV seasons running from May to October relative to a currently estimated time point 0 in Nov 2013.

Recruitment on both Hemispheres will include a period of 'On Season' recruitment and a period of 'Off Season' recruitment and a third period of recruitment matching the first period.

An interim analysis data lock is scheduled after 1.5 years or in June 2015, whichever occurs first.

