3.2. Secondary objectives

In a cohort of infants followed-up from birth up to 2 years of age;

- To determine the total health burden of non-RSV-associated RTI with a suspicion of involvement of the lower respiratory tract.
- To evaluate the association between RSV-associated LRTI, RSV-associated severe LRTI and RSV neutralizing antibodies in the baseline cord blood samples collected from subjects, at birth.
- To determine the prevalence of RSV infection, at 2, 4, 6, 12, 18 and 24 months in a randomly selected sub-cohort of subjects by assessing antibodies in serum.
- To assess the between calendar year variability in the incidence rates of RSV-associated LRTI.

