4.2. Secondary endpoints

- Levels of RSV neutralizing antibodies in the cord blood samples collected at birth.
- Levels of RSV neutralizing antibodies in the blood samples collected at 2, 4, 6, 12, 18 and 24 months.
- Occurrence of LRTI/severe LRTI cases as classified by the LRTI case definition and severity scale, in the subgroups of subjects recruited from Months 1-6 and 13-18.

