12.3.2. Secondary incidence analysis

12.3.2.1. (SO1) To determine the total health burden of non-RSV-associated RTI with a suspicion of involvement of the lower respiratory tract

Template 15 Incidence rate of first episode of [RTI with suspicion of involvement of LRT (all cause), WHO LTRI (all cause), WHO severe LRTI (all cause)], by age interval – overall and by country (PPS)

						95%	exact CI
Country	Age interval (Months)	Total number of subjects	Total number of first episode (all cause)	Total number of person- years	Incidence rate (100 person- years)	LL	UL
Overall	0-5						
	6-11						
	0-11						
	12-23						
	0-23						
<each country=""></each>							

Incidence rate computed using the number of first episode (all cause) as numerator and the total number of personyears over the age interval as denominator

CI=confidence interval, LL, UL for incidence = Exact 95% Lower and Upper confidence limits 95% CI computed using exact method for first episode incidence

Template 16 Monthly distribution of WHO RSV LRTI – by country (PPS)

	AR (N=)	BD	(N=)	CA	A (N=)	FI	(N=)	HN	(N=)	SA	(N=)	Tł	H (N=)	US	(N=)
Calendar Month	n	%	Ν	%	n	%	n	%	n	%	n	%	n	%	n	%
January																
February																
March																
April																
Мау																
June																
July																
August																
September																
October																
November																
December																

N=number of WHO RSV LRTI episode for each country

n (%) = total number and percent of WHO RSV LRTI episodes for each month

AR = Argentina

BD = Bangladesh

- CA = Canada
- FI = Finland

HN = Honduras

SA = South Africa

TH = Thailand

US = US

- 12.3.3. Tertiary incidence analysis
- 12.3.3.1. (TO5) To assess the impact of potential RSV risk factors (e.g. complications at birth, family history of respiratory disease, living environment and household composition, breast feeding, passive smoking, day care attendance) on the incidence and severity of RSV-associated LRTI.
- Template 17 Potential risk factors for first [WHO RSV LRTI WHO RSV severe LRTI] episode, evaluated in [Univariate – Multivariate] Cox model analysis for first [WHO RSV LRTI – WHO RSV severe LRTI] episode, over the 2 year follow-up period (PPS)

Characteristics	Category	Number of Observations		Hazard		Global n-
		model	Event	(95% CI)	p-value	value
RSV-A maternal antibodies levels in cord blood	Seronegative					
	Seropositive					
	Missing					

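### The SAP has no analysis of the between-calendar-year objective, and the protocol's contrast for it is diluted because the two recruitment groups share half of their follow-up time

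*Protocol*

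**What the plan says.** The objective is worded the same way in protocol 2.1.2 and SAP 3.2: "To assess the between calendar year variability in the incidence rates of RSV-associated LRTI".

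Protocol 9.7.2 gives the method. RSV LRTI and severe LRTI, classified by the study's own (GSK) definition and severity scale, are counted over child-years "in the subgroups of subjects recruited from months 1-6 and from months 13-18". No age band, season or calendar year is attached to the numerator or the denominator.

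Protocol 3.1 sets follow-up at "Approximately 2 years for each participant enrolled in the primary study". Protocol 9.11 records that, after the interim analysis, "it was decided that the incidence rate would be more robust if all subjects completed the primary study until 2 years of age". The later recruits are therefore also followed for the full period.

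Protocol Appendix C shows why those two blocks were chosen. Its list of recruitment periods includes "Subjects from NH during third 6 months; repeat of first 6 months NH", with a matching line for the South.

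The SAP repeats the endpoint in 4.2, "in the subgroups of subjects recruited from Months 1-6 and 13-18", and then takes it no further:
- Table 3 sends secondary endpoints only to 6.6.2 (all-cause incidence), 6.9.1 and 6.9.2 (antibodies).
- The subgroup lists in 6.3 and 6.4 contain neither recruitment block nor calendar year.
- The mock outputs for secondary objectives carry the labels SO1 to SO3 only.
- Section 9 lists changes from the protocol without naming this objective. It does restrict subgroup analysis to country, and it removes incidence rates by the GSK definition, which is the scale the endpoint uses.

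**The concern.** There are two linked problems. First, the analysis plan for the 2-year data produces no estimate for an objective that it still lists. The nearest outputs do not fill the gap: Template 12 splits by length of in-season exposure, and Template 16 tabulates episodes by calendar month with no year and no person-time.

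Second, going back to protocol 9.7.2 would not fully repair this. A rate over all child-years averages the season that differs between the blocks with seasons that both blocks live through, so a real year-to-year difference is understated.

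The protocol's rationale (1.2) says the results may later be used to evaluate incidence reduction after a vaccine is introduced. A reader doing that needs some idea of ordinary variation between years.

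**Working it through.** The documents state no effect size, precision or sample size for this comparison, so there is no planned figure of that kind to reproduce. The enrolment figure used below does reproduce: 1920 / (1 - 0.20) = 2400.

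**Inputs**
- Births spread evenly over study months 0-6 (block 1) and 12-18 (block 2), each child followed for 24 months.
- Seasons from Appendix C, with month 0 in November 2013. North: months 0-6, 12-18, 24-30, 36-42 (S1-S4). South: 6-12, 18-24, 30-36 (S1-S3).
- Assumed example: S1 has twice the intensity of every later season, so the true ratio is 2.0.

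**Calendar overlap.** A child born at month u is followed from u to u+24. The matched child is followed from u+12 to u+36. They share 12 of 24 months, or 50%.

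**In-season months per child (averages)**
- North, block 1: S1 = mean(6-u) = 3, S2 = 6, S3 = mean(u) = 3. Block 2: 3, 6, 3 in S2, S3, S4. Two of each block's three seasons are common.
- South, block 1: 6 in S1 and 6 in S2. Block 2: 6 in S2 and 6 in S3. One of two seasons is common.

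**Ratio over 24 months, constant hazard**
- North: (3×2 + 6 + 3) / 12 = 15/12 = 1.25.
- South: (6×2 + 6) / 12 = 18/12 = 1.50.

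**Ratio over 24 months, hazard falling with age.** Weights are 1 : 0.35 : 0.08 for ages 0-5, 6-11 and 12-23 months, close to the Table 12 row 44.1 / 15.0 / 3.7. These are hospitalization rates used as a proxy for LRTI.
- North: S1 = 3×1 = 3.00; S2 = 3×0.35 + 3×0.08 = 1.29; S3 = 3×0.08 = 0.24; total 4.53. S1 share = 3.00/4.53 = 0.66, ratio = 1 + 0.66 = 1.66.
- South: S1 = 3×1 + 3×0.35 = 4.05; S2 = 6×0.08 = 0.48; total 4.53. S1 share = 0.89, ratio = 1.89.
- Across the three Table 12 rows that give all three age bands, the ratio is 1.62-1.69 (North) and 1.80-1.97 (South).

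**Another pattern.** If seasons alternate 2:1 and the hazard is constant, the North gives (3×2 + 6×1 + 3×2) / (3×1 + 6×2 + 3×1) = 18/18 and the South gives (6×2 + 6×1) / (6×1 + 6×2) = 18/18. The ratio is 1.00 in both. With the Table 12 weights it is 1.32-1.34 (North) and 1.51-1.91 (South).

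**Restricting age.** At 0-5 months, block 1 occupies study months 0-12 and block 2 months 12-24, so no calendar time is shared. On the Appendix C calendar each block has 3.0 in-season months per child, all in its own season, and the ratio is 2.0 in both hemispheres. At 0-11 months the South still shares no season (6 months in S1 against 6 in S2). The North does share one: (3×2 + 3)/6 = 1.50 with a constant hazard.

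**Precision at 0-5 months.** Assume 1920 evaluable children, one-third in each block (640), and the SAP's eight countries of equal size. That gives 80 children, or 40 child-years, per block and country. Apply protocol 9.3's factor of 8 to Table 12's 16.9-44.1 hospitalizations per 1000. With n cases in each block, the 95% CI factor is exp(1.96×√(2/n)), ignoring clustering.

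| Unit | Child-years per block | Cases per block | CI factor |
|---|---|---|---|
| One country | 40 | 5.4-14.1 | 3.3-2.1 |
| South, 2 countries | 80 | 10.8-28.2 | 2.3-1.7 |
| North, 3 countries | 120 | 16.2-42.3 | 2.0-1.5 |

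**The case against.** The best defence has four parts.

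First, the dilution is easy to exaggerate. A reader might infer that the two groups live through mostly the same RSV seasons and that the contrast is close to worthless. The documents do not support that. Calendar overlap is half, and so is in-season overlap in the South. In the North, 75% of in-season time lies in seasons common to both blocks, but the blocks meet those seasons at different ages. Weighted by Table 12, the season-by-season overlap of expected events is 31-38% (North) and 3-20% (South). Counting first episodes only, as the SAP does, would reduce the dilution further. This part stands: with a realistic age gradient the loss is moderate in the North and small in the South.

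Second, SAP section 9 is not silent. Limiting subgroups to country and dropping GSK-scale incidence together remove the endpoint as specified. That is true, but a reader must infer it, because the objective is never named and 3.2 and 4.2 still list it. SAP section 10 refers to a separate list of tables, not among the documents here. A title in that list would still have no method in the SAP.

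Third, Template 16 is not offered as the between-year analysis, so faulting it for lacking years is beside the point. This stands.

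Fourth, everything is descriptive, and country-level counts will be small. A reader might infer that the collected data would settle the question in each country. The interval factors above say otherwise. This limits what the table can show, but it does not justify leaving a listed objective without output.

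**Conclusion.** The concern holds in this form. The firmer part is the omission: the SAP retains a secondary objective and its endpoint, analyses neither, and does not say that the objective is dropped. The second part is that protocol 9.7.2 compares groups sharing half of their calendar time, which pulls the ratio towards 1. In the assumed example a true 2.0 appears as 1.25 (North) or 1.50 (South) with a constant hazard, and as about 1.66 or 1.89 with age weighting.

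The ratios rest on even recruitment without delay, all events falling in season, hospitalization rates standing in for the LRTI age gradient, and the Appendix C calendar. SAP 6.1.4.5 and Table 10 give the reverse months for the two hemispheres, and the two documents should be reconciled. The 50% calendar overlap, and the absence of shared calendar time at age 0-5 months, do not depend on which season calendar is used. For the three countries the SAP treats as having year-round transmission, only these calendar statements apply.

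**What to change.** Add one descriptive table to SAP 6.6: incidence rate of first WHO RSV LRTI and first WHO RSV severe LRTI at age 0-5 months, recruited in months 1-6 against months 13-18, with rate ratio and 95% CI. Show it by country and pooled within hemisphere, because country counts will be small. Age 0-11 months may be added for the South.

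Use the same month-matched blocks in Bangladesh, Honduras and Thailand. Calendar year of birth would not do there: 18 months of recruitment from November 2013 gives births in November-December 2013, all of 2014 and January-April 2015, so year would be confounded with birth month.

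State in section 9 that the scale changes from GSK to WHO, that the age window is restricted, and that pooling within hemisphere is an exception to the by-country rule. Protocol 9.10 allows such a change if the study report describes and justifies it, so an amendment of 9.7.2 is not essential. Adding year and person-time to Template 16 is optional.

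The cost is one table from data already collected. The downside is fewer cases than over 0-23 months and wide intervals by country, although Table 12 puts the highest rates at 0-5 months. If the sponsor does not want the analysis, section 9 should declare the objective dropped.

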9.7.3. Tertiary Objectives

• To explore the association of co-infections with the incidence of RSV-associated LRTI and/or severe LRTI (as determined by the LRTI case definition and severity scale) using xTAGTM RVP Fast assay.

For each of the other respiratory viruses, incidence rates will be calculated as the number of RSV-associated LRTI/severe LRTI cases associated co-infected with the virus over the number of children-years observations.

• To explore the association of RSV and other respiratory viruses with the incidence of LRTI and/or severe LRTI (as determined by the LRTI case definition and severity scale) using xTAGTM RVP Fast assay.

For each of the respiratory viruses, incidence rates will be calculated as the number of LRTI/severe LRTI cases associated with the virus over the number of children-years observations.

• To explore the association of RSV viral load with the incidence of RSVassociated RTI, LRTI and/or severe LRTI (as determined by the LRTI case definition and severity scale).

Descriptive analyses (mean, median, min, max) of viral load assessed by the RSV RTqPCR of RSV RTI, RSV LRTI and severe LRTI cases will be tabulated.

• To explore the impact of changes to the symptoms and threshold levels of symptoms in the LRTI case definition and severity scale.

Frequency tables will summarize the proportion of RSV-associated LRTI/ severe LRTI cases associated with a list of symptoms and clinical parameters, overall and by age categories.

This will help us to determine potential areas of improvement of the LRTI case definition and severity scale. Incidence rates of RSV-associated LRTI/severe LRTI will be calculated for any proposal of modification of the LRTI case definition and severity scale.

• To explore the impact of variations in cord-blood sample collection variables on the stability of test results.

The measured maternal antibody levels will be assessed versus variability in sample collection variables. This involves assessment versus various continuous and categorical variables and an overall comparison between samples as classified 'according to recommended procedure' and 'not according to recommended procedure'.

The measured maternal antibody levels by duration of the processing step and overall process duration will be analysed graphically and by log-linear regression.

The measured maternal antibody levels by storage condition or tube type will be analysed graphically and by group statistics (mean, 95% CI). Group means will be compared by t-test to assess the statistical significance of differences.

The measured maternal antibody levels in samples collected 'according to recommended procedure' and 'not according to recommended procedure' will be analysed graphically and by group statistics (mean, 95% CI). Group means will be compared by t-test to assess the statistical significance of any difference.

• To assess the impact of potential RSV risk factors (e.g. complications at birth, family history of respiratory disease, lifestyle characteristics and household composition, breast feeding, passive smoking, day care attendance) on the incidence and severity of RSV-associated LRTI.

The incidence of any, severe, non-severe RSV-associated LRTI will be analysed using a Poisson regression model including potential risk factors.

• To assess the natural decay of maternal antibody levels using a single follow-up blood sample collected from a randomly selected sub-cohort of subjects at 2, 4, 6, 12, 18 and 24 months.

The primary analysis will be based on ATP sub-cohort for this objective.

The decay of maternal antibody levels over time will be analysed graphically and by a log-linear regression. A true, natural decay curve will be explored by stochastically reducing the sample to uninfected subjects only. The following steps will be taken to identify, confirmed and suspected infected subjects to eliminate these from the sample;

- Subjects with an RSV positive nasal swab during the study before time of sampling will be eliminated.
- A sensitivity analysis of the decay curve will be explored in sub-sample consisting of the subjects born 'off-season' as these have the lowest likelihood of having been infected.
- Subjects with an antibody titer at the sampling time that is more than 2-fold above the expected value based on their baseline (cord blood) value and the established decay curve will be considered to have been infected, eliminated and the decay curve refined.
- Step 3 is repeated up to 5 times until the most accurate decay curve is established.

